4.6 PATIENT, STUDY, AND SITE DISCONTINUATION

4.6.1 Patient Discontinuation from the Study

Patients are required to complete an early termination visit as soon as possible after they decide to withdraw from the study or the investigator withdraws the patient from the study. This visit can be performed remotely.

Patients have the right to voluntarily withdraw from the study at any time for any reason. In addition, the investigator has the right to withdraw a patient from the study at any time.

Reasons for patient discontinuation from the study may include, but are not limited to, the following:

- Patient withdrawal of consent
- Study termination or site closure
- Adverse event
- Loss to follow-up
- Patient non-compliance, defined as failure to comply with protocol requirements as determined by the investigator or Sponsor

Every effort should be made to obtain a reason for patient discontinuation from the study. The primary reason for discontinuation from the study should be documented on the appropriate eCRF. If a patient requests to be withdrawn from the study, this request must be documented in the source documents and signed by the investigator. Patients who withdraw from the study will not be replaced.

If a patient withdraws from the study, the study staff may use a public information source (e.g., county records) to obtain information about survival status.

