6. STATISTICAL CONSIDERATIONS AND ANALYSIS PLAN

The final analysis of the study will occur at the end of the study (see Section 3.2).

Differential loss to follow-up may introduce bias into the study. Patients may be lost to follow-up because they are fully recovered or they experience an adverse outcome.

Details of the statistical analysis methods and endpoints will be described in the study Statistical Analysis Plan (SAP) which will be finalized prior to study completion.

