6.4 STATISTICAL ANALYSES

The analysis population will consist of all patients enrolled in the study. Long-term clinical and PROs will be summarized descriptively and trends over time will be explored. Outcomes may also be explored by patient characteristics (e.g., treatment received in the parent study), as appropriate.

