6.4.2 Secondary Endpoints

The secondary endpoints are as follows:

- Impact of dyspnea symptoms on specific activities, as assessed through use of PROMIS-Dyspnea Questionnaire at Day 1 and Months 1, 2, 3, 4, 5, and 6
- Respiratory-specific health-related quality of life, as assessed through use of SGRQ at Day 1 and Months 1, 2, 3, 4, 5, and 6
- Proportion of patients with COVID-19-related medically-attended visits through to study end (defined as hospitalization, ER visit, urgent care visit, physician's office visit, or telemedicine visit with the primary reason for the visit being COVID-19 or COVID-19-related symptoms)
- Proportion of patients with all-cause mortality

- Proportion of patients with death attributable to progression of COVID-19
- Proportion of patients re-infected with SARS-CoV-2
- Proportion of patients with any post-treatment infection including but not limited to bacterial, viral, or fungal pneumonia or sepsis
- Frequency of COVID-19-related complications (e.g., death, hospitalization, radiologically-confirmed pneumonia, acute respiratory failure, sepsis, coagulopathy, pericarditis, myocarditis, cardiac failure)
- Incidence and severity of adverse events and serious adverse events, with severity determined according to NCI CTCAE v5.0

Observed absolute values will be summarized by means, standard deviations, medians, and ranges for continuous endpoints, as appropriate, while count and percentages will be tabulated for categorical endpoints by study timepoints. Longitudinal modeling of endpoints may also be explored, as appropriate.

All endpoints will be summarized descriptively and no p-values will be presented.

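### The survival check is optional, has no stated step for patients lost to follow-up, and comes with no rule for unknown status, so both mortality proportions may be understated

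*Combined protocol and SAP*

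**What the plan says.** **Survival check (section 4.6.1).** The only provision for learning vital status after a patient leaves is that, if a patient withdraws, "the study staff may use a public information source (e.g., county records) to obtain information about survival status". The verb is permissive and the stated trigger is withdrawal. The same section names "Loss to follow-up" as a reason for discontinuation distinct from withdrawal of consent, and attaches no survival step to it. The schedule of activities (Appendix 1) has no vital-status item at Month 6.

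**Endpoints (section 6.4.2).** Two secondary endpoints depend on vital status: "Proportion of patients with all-cause mortality" and "Proportion of patients with death attributable to progression of COVID-19". The summary method is that "count and percentages will be tabulated for categorical endpoints by study timepoints". Section 6.4 adds: "The analysis population will consist of all patients enrolled in the study". Neither section says what happens to a patient whose vital status is unknown, and no censoring method is named.

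**Acknowledged risk (section 6).** The protocol warns of bias from differential loss and explains: "Patients may be lost to follow-up because they are fully recovered or they experience an adverse outcome". It sets out no remedy for mortality. Analysis detail is deferred to a separate SAP that is not part of the text reviewed.

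**Death reporting (sections 5.3.1 and 5.3.5.4).** Deaths from Day 1 to the end of the study must be recorded and reported at once. These sections do not say how a site would learn of a death once contact has ended.

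**The concern.** A proportion over all enrolled patients is only as good as the vital-status information behind it. If contact ends and nobody is required to look, a later death stays in the denominator and never enters the numerator. The protocol recognises that some patients may be lost because things went badly for them, which is the group in which an unseen death is most plausible.

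Few deaths may be expected in a six-month follow-up of this size, so one or two missed deaths could shift both proportions noticeably in relative terms. Deaths are also summarised in the safety analysis, which may be explored by parent-study treatment (section 6.5), and interim safety analyses may support a marketing application (section 6.7). The absence of p-values therefore does not make ascertainment unimportant. With about 180 sites (section 9.5), an optional check may also be applied unevenly.

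**Working it through.** **Inputs from the protocol.** N is about 1040, set by site feasibility (section 6.1). Follow-up is about 6 months. No expected mortality, loss rate or target precision is stated, so there is no figure of the plan's own to reproduce. What follows is an illustration on assumed values.

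**Assumed quantities.** p = mortality in followed patients; d = share lost, with none of their deaths found; R = mortality in lost patients divided by mortality in followed patients. R runs from 0.5 to 5, because section 6 names recovery as well as adverse outcome as a reason for loss.

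**Step 1. Undetected deaths as non-events, all enrolled as denominator.**
- True proportion = p(1 − d) + R·p·d
- Reported proportion = p(1 − d)
- Relative understatement = R·d / (1 − d + R·d), in which p cancels

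At d = 10%: R = 0.5 gives 0.05/0.95 = 5.3%; R = 1 gives 0.10/1.00 = 10.0%; R = 2 gives 0.20/1.10 = 18.2%; R = 5 gives 0.50/1.40 = 35.7%.

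| Share lost | R = 0.5 | R = 1 | R = 2 | R = 5 |
|---|---|---|---|---|
| 5% | 2.6% | 5.0% | 9.5% | 20.8% |
| 10% | 5.3% | 10.0% | 18.2% | 35.7% |
| 20% | 11.1% | 20.0% | 33.3% | 55.6% |

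Under this handling the error is never upward.

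**Step 2. The same in counts, with p = 1% and d = 10%.** Lost patients: 0.10 × 1040 = 104; followed: 936. Deaths seen: 0.01 × 936 = 9.4, reported as 0.90%. Deaths missed: 0.01 × 104 × R = 0.5, 1.0, 2.1 and 5.2 for R = 0.5, 1, 2 and 5. The true proportion is then 0.95%, 1.00%, 1.10% and 1.40%.

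**Step 3. Scale against sampling error.** At p = 1% the 95% half-width is 1.96 × √(0.01 × 0.99 / 1040) = 0.60 percentage points. The shortfalls in step 2 are 0.05, 0.10, 0.20 and 0.50 points, all smaller than that.

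**Step 4. Known-status patients as denominator instead.** The estimate is p, with relative error 1/(1 − d + R·d) − 1. At d = 10% this is +5.3%, 0%, −9.1% and −28.6% for R = 0.5, 1, 2 and 5. The direction now depends on who is lost.

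**Step 5. What analysis alone can do.** With p = 1% and d = 10%, best-case and worst-case bounds run from 9.36/1040 = 0.90% to (9.36 + 104)/1040 = 10.9%. Their width equals d. Only finding out vital status narrows them; an analysis rule cannot.

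**The case against.** A reader might infer that lost patients are counted as survivors and that both mortality endpoints are therefore biased low. The documents do not support that as a statement of fact. Nothing says that unknown status is treated as alive; handling is unspecified and left to the SAP. Downward bias is certain only if all enrolled patients form the denominator and at least one death goes undetected. With a known-status denominator (step 4), the direction is open. Section 6 names full recovery alongside adverse outcome, so it does not establish that those lost are at higher risk.

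Other counter-arguments have weight:
- Section 4.6.1 speaks of the investigator withdrawing a patient and says that patients who withdraw are not replaced. Withdrawal could thus be meant to cover every discontinuation, including loss to follow-up. The exclusion is a literal reading, not an explicit rule. On the wider reading the check is still optional.
- Every death that a site learns of in the reporting period must be recorded. Weekly diaries, monthly visits and a required early termination visit should expose lapses in contact quickly, and section 6.2 reports disposition. Only deaths that no site hears of are missed.
- The SAP can choose the estimator. That is so, but it cannot recover vital status that was never collected, so collection has to be settled in the protocol.
- These are secondary, descriptive endpoints, and the illustrated shortfall at 10% loss lies within sampling error. That limits the priority. Unlike sampling error, however, the shortfall is systematic and the planned summaries would not show it.

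**Conclusion.** The point stands as a gap in ascertainment with a likely, not certain, downward effect. The survival check is optional; read literally, it does not extend to patients lost to follow-up; and no rule covers unknown status. Under the plan's default tabulation, an undetected death would be a non-event, and both mortality proportions may be understated.

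The size cannot be derived from the documents. At an assumed 10% loss with no deaths found among those lost, the relative understatement is about 5% to 36% for mortality ratios of 0.5 to 5, and 10% at a ratio of 1. If some of these deaths come to light by other routes, it is smaller. The change is worth making because it is cheap and cannot be made retrospectively by analysis. It does not affect the primary symptom-diary endpoint.

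**What to change.** 1. In section 4.6.1, replace the optional wording with a requirement such as: *Where local law and consent permit, study staff will check available public records for survival status at Month 6 for every patient who withdraws or is lost to follow-up.*
2. Report the number of patients with unknown vital status beside both mortality endpoints.
3. In the SAP, estimate all-cause mortality by Kaplan-Meier with censoring at the date last known alive, and give best-case and worst-case bounds for unknown status. The bounds are needed because Kaplan-Meier assumes that censoring is unrelated to risk, which section 6 puts in doubt.

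**Cost.** Site staff would do the lookups. At an assumed 10% loss, 104 patients over about 180 sites is 104/180 ≈ 0.6 lookups per site. Records may not be accessible in some countries, so some unknowns will remain and the bounds may stay wide. Public records may not give cause of death, so the gain is firmest for all-cause mortality; COVID-19 mortality should carry that limitation explicitly.

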4.6.2 Study Discontinuation

The Sponsor has the right to terminate this study at any time. Reasons for terminating the study may include, but are not limited to, the following:

- Patient enrollment is unsatisfactory

The Sponsor will notify the investigator if the Sponsor decides to discontinue the study.

4.6.3 Site Discontinuation

The Sponsor has the right to close a site at any time. Reasons for closing a site may include, but are not limited to, the following:

- Excessively slow recruitment
- Poor protocol adherence
- Inaccurate or incomplete data recording
- Non-compliance with the International Council for Harmonisation (ICH) guideline for Good Clinical Practice
- No study activity (i.e., all patients have completed the study and all obligations have been fulfilled)

5. ASSESSMENT OF SAFETY

5.1 SAFETY PLAN

Any adverse events that occur during this study should be reported as outlined below.

For ongoing adverse events starting in the parent study, any follow-up of the adverse event will be reported in this study (Study CV43140). The adverse event severity, according to NCI CTCAE v5.0 ([Table 2](#)), should be evaluated by the investigator at the Day 1 visit of this study and recorded in the "adverse event initial NCI CTCAE grade" field of the Adverse Event eCRF for Study CV43140. The most extreme NCI CTCAE grade for the adverse event should also be recorded, taking into account the severity of the event since it was first reported during the parent study.

Please note that "study drug" refers to the treatment administered in the parent study prior to this follow-up study.

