4.2 METHOD OF TREATMENT ASSIGNMENT AND BLINDING

This is a non-randomized, observational, and non-treatment study. After initial written informed consent has been obtained, all screening procedures and assessments have been completed, and eligibility has been established for a patient, the study site will set up the patient in the electronic data capture (EDC) system with the same patient identification number as from the parent study.

The treatment arm to which patients were assigned in the parent study will not be disclosed until the final analysis of the parent study is reported, which may occur during this study (CV43140).

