4.5.2 Medical History, Baseline Conditions, Concomitant Medication, and Demographic Data

Medical history, demographic data, concomitant medications, and resolved adverse events may be transferred from the parent study. Ongoing adverse events at the end of the parent study will be reopened in this study (CV43140) (see Section [5.1](#)).

In addition, all concomitant medications (e.g., prescription drugs, over-the-counter drugs, vaccines, herbal or homeopathic remedies, nutritional supplements) and supplemental oxygen used by the patient during the study will be recorded. At each visit, changes in concomitant medication and allergies will be recorded.

Any COVID-19 vaccination that has occurred before the patient enrolls into the study or during the study will be recorded on the Concomitant Medications eCRF, including the report product or brand/trade or company manufacturer, if available (examples: Pfizer COVID-19 vaccine, Moderna COVID-19 vaccine), and date(s) administered if known. If not available, report as COVID-19 vaccine.

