5.3.5.3 Persistent or Recurrent Adverse Events

A persistent adverse event is one that extends continuously, without resolution, between patient evaluation timepoints. Such events should only be recorded once on the Adverse Event eCRF. The initial severity (intensity or grade) of the event will be recorded at the time the event is first reported. If a persistent adverse event becomes

more severe, the most extreme severity should also be recorded on the Adverse Event eCRF. If the event becomes serious, it should be reported to the Sponsor immediately (i.e., no more than 24 hours after learning that the event became serious; see Section 5.4.2 for reporting instructions). The Adverse Event eCRF should be updated by changing the event from "non-serious" to "serious," providing the date that the event became serious, and completing all data fields related to serious adverse events.

A recurrent adverse event is one that resolves between patient evaluation timepoints and subsequently recurs. Each recurrence of an adverse event should be recorded as a separate event on the Adverse Event eCRF.

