6.5 SAFETY ANALYSES

The safety analyses will include all enrolled patients in the study.

Safety will be assessed through descriptive summaries of serious adverse events (nature, frequency, and severity) and vital signs. Serious adverse events will also be listed. Safety may be explored by study treatment received in the parent study, as appropriate.

All verbatim adverse event terms will be mapped to Medical Dictionary for Regulatory Activities thesaurus terms, and adverse event severity will be graded according to NCI CTCAE v5.0. All adverse events, including serious adverse events that are continuing/persisting from the parent study (regardless of causal association with the study drug administered in the parent study) or any new adverse event with an onset date on or after the first day of enrollment and during this follow-up study, will be summarized by mapped term, appropriate thesaurus level, and severity grade. For events of varying severity, the highest grade will be used in the summaries. Deaths and cause of death will be summarized.

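### As written, an adverse event carried over from the parent study can enter the follow-up severity summary at a grade it reached only before Day 1

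*Combined protocol and SAP*

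**What the plan says.** Section 4.5.2: "Ongoing adverse events at the end of the parent study will be reopened in this study".

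Section 5.1 describes two grades for such an event. The severity that "should be evaluated by the investigator at the Day 1 visit of this study" goes into the initial-grade field. The most extreme grade is recorded as well, "taking into account the severity of the event since it was first reported during the parent study".

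Section 6.5 covers "All adverse events, including serious adverse events that are continuing/persisting from the parent study", together with new events that start on or after enrollment. Both are summarized by mapped term, thesaurus level and grade. On grade it says: "For events of varying severity, the highest grade will be used in the summaries". The only split it mentions for safety is an optional one by parent-study treatment.

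These summaries serve the secondary endpoint in Section 6.4.2: "Incidence and severity of adverse events and serious adverse events". Section 2 states the purpose of the study as evaluating long-term sequelae over about 6 months from the end of the parent study. Section 6 leaves analysis detail to a SAP that is to be finalized before the study is completed.

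**The concern.** The two grade fields for a carried-over event cover different periods. The initial grade starts at Day 1; the most extreme grade starts at first report in the parent study. A summary that takes the higher value can therefore show a grade that belongs to the parent-study period in a table read as follow-up experience. Events already present at Day 1 also enter a summary labelled incidence.

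What is at stake is what the table describes. A reader could take a parent-study peak for a severe event during long-term follow-up, or could fail to tell an event that had improved before Day 1 from one that got worse after it. The table split can be decided later. A grade that is never collected cannot be added later, so the recording rule in Section 5.1 is the more urgent part.

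**Working it through.** The plan states no figure to reproduce, so the check sets the recording rule beside the summary rule.

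**Inputs**
- d = grade at Day 1 (Section 5.1, initial-grade field).
- p = highest grade from first report in the parent study up to and including Day 1, so p ≥ d.
- f = worst grade on or after Day 1, so f ≥ d.
- m = recorded most extreme grade. Under Section 5.1, m = max(p, f).
- Summarized grade (Section 6.5): the highest grade, taken here to be m. This is an inference. Section 6.5 names no field, but d and m are the only grades that Section 5.1 defines for these events.

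**Step 1: the grade shown against the grade reached in follow-up**

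| Course of event | p | d | f | Recorded (d, m) | Shown as | Worst in follow-up |
|---|---|---|---|---|---|---|
| Improved before Day 1, then stable | 3 | 1 | 1 | 1, 3 | 3 | 1 |
| Improved, then partly worsened | 3 | 1 | 2 | 1, 3 | 3 | 2 |
| Mild until Day 1, then worsened | 1 | 1 | 3 | 1, 3 | 3 | 3 |
| Stable throughout | 2 | 2 | 2 | 2, 2 | 2 | 2 |

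The shown grade exceeds the follow-up grade exactly when p > f. Otherwise the look-back changes nothing. The first three rows leave the same pair of recorded grades.

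**Step 2: comparison with the general rule.** Section 5.3.5.3 records a persistent event once, with the grade when first reported and, if it becomes more severe, the most extreme grade. There both fields start at the same point, so m above the initial grade means worsening. Section 5.1 moves the start of one field to Day 1 and not the other, so that reading no longer holds for carried-over events.

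**Step 3: can the follow-up grade be recovered?** Patients are set up "with the same patient identification number as from the parent study" (Section 4.2), so p could be linked from parent records, although no section plans this.
- If m = d, then f = d, even without linkage.
- If p = d, then f = m.
- If m > p, then f = m.
- If p > d and m = p, then f may be any grade from d to p. With d = 1, p = 3 and m = 3, f may be 1, 2 or 3.

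So linkage resolves some records but not the last kind, and every over-graded event is of that kind, because p > f gives m = p and f ≥ d gives p > d.

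**Step 4: serious events.** If a persistent event becomes serious, Section 5.3.5.3 calls for "providing the date that the event became serious". Table 2 (Section 5.3.3) requires Grade 4 events to be reported as serious, and Section 5.4 requires significant follow-up information on serious events within 24 hours. A return to Grade 4 should therefore leave a report. The claim of non-recovery is limited to non-serious events.

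**Step 5: scale.** No adverse event rates are given. At the planned 1040 patients, each patient shown at Grade 3 or above solely because of a parent-study peak adds 1/1040 = 0.096 percentage points. This is a unit of scale, not an estimate.

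**The case against.** The strongest reply is that this is an openly stated choice. Section 6.5 says that continuing events are included. The adverse event objective in Section 2 is not limited to events that start after Day 1, and persisting events matter to a study of sequelae. That stands: including carried-over events, and keeping an all-time peak, is legitimate. What it does not justify is presenting that peak as severity during follow-up.

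Second, Section 6.5 does not say that the look-back field supplies the highest grade, nor that continuing and new events share one table. A reader might infer that the plan commits to a single pooled table with misattributed grades. The text does not go that far. It includes both groups, names no split and places no period limit on the grade.

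Third, detail is deferred to the SAP, and onset date already separates the two groups. This answers the missing split. It does not answer the missing grade. A worst follow-up grade may exist in the eCRF or in medical records, since Section 5.3.1 has events sought at each contact, but no section requires dated grade changes.

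Fourth, Section 5.3.5.6 keeps anticipated COVID-19 fluctuations out of adverse event reporting, which reduces the pool of carried-over events by an unknown amount.

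Fifth, counting only new-onset events as incidence would drop carried-over events that worsen after Day 1, although Section 5.2.1 treats worsening of a known condition as an adverse event. This is right, and the fix below allows for it.

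**Conclusion.** The point holds as a minor one. Under the stated rules a carried-over event can appear in the follow-up severity summary at a grade reached only in the parent study, and the two described grade fields cannot tell improvement before Day 1 from worsening after it. This rests on two assumptions: that the highest grade in Section 6.5 is the recorded most extreme grade, and that the eCRF does not capture a worst grade since Day 1 elsewhere.

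The size is unknown, and it is zero where no parent-study peak exceeds the worst grade from Day 1 onward. A reader might infer that reported severity will be materially inflated. The documents give no rates from which to say so. Nor is any test at risk: Section 6.4.2 presents all endpoints descriptively and without p-values. The effect is on the interpretation of one secondary safety summary.

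**What to change.** **Section 6.5 (or the SAP).** Present events that are new or worsened since Day 1 as the follow-up incidence. Show carried-over events separately, with the Day 1 grade against the worst grade on or after Day 1. Keep the pooled table as supplementary. State which recorded grade each table uses.

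**Section 5.1.** Record the most extreme grade since Day 1, if the eCRF does not already capture it, and keep the all-time peak as a separate item.

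**Cost.** Wording changes, one table split and at most one extra eCRF field, with no added patients or visits. The drawback is smaller table cells. The field is best settled before data collection is far advanced, because the split can be made afterwards and the missing grade cannot.
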